## 9.4.2 **Duration of SOM in the ITT Population**

Using the same definition and statistical method as for primary endpoint, the duration of SOM will be compared between treatment groups in the ITT population.

#### 9.4.3 **Duration of UOM**

UOM is defined as a WHO score  $\geq$ 2. The duration of UOM is defined as the number of days from the first WHO score  $\geq$ 2 to the first day with WHO score  $\leq$ 2 with no further occurrence of WHO score  $\geq$ 2. A log-rank test will be used to compare the duration of UOM between the two treatment groups.

Resolution of UOM is defined as the first assessment with a WHO score <2 with no further reports of a WHO grade of  $\ge 2$ . If the patient has not met the requirements for resolution of UOM by the 6-week post-RT visit, he/she will be considered censored at that visit (or the point of discontinuation from the study, if the patient discontinues prior to that time point). For statistical reasons, patients who do not experience UOM will be treated as having a duration of 0.01 days.

#### 9.4.4 Incidence of SOM

The incidence of SOM will be calculated as the percent of patients within each treatment group who have at least one WHO score ≥3. The incidence of patients with SOM will be compared between treatment groups using the chi-square test.

#### 9.4.5 Quality of Life

A Quality of Life Questionnaire will be completed by each patient at Baseline, 4 weeks and end of study drug treatment (2 weeks post-RT). The EORTC QLQ-C30 (version 3) and the EORTC QLQ-H&N43 instrument will be used for these assessments. 12 multiple-item scales (fear of progression, body image, dry mouth and sticky saliva, pain in the mouth, sexuality, problems with senses, problems with shoulder, skin problems, social eating, speech, swallowing, and problems with teeth) and 7 single-

item scales (coughing, lymphoedema, neurological problems, trismus, social contact, weight loss, and problems with wound healing) will be computed and summarized by visit, including change from baseline.

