10.2. Secondary Efficacy Endpoints

10.2.1 Primary Secondary Analyses

The primary secondary endpoints are listed below in hierarchical order and will be compared in the mITT population.

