10.2.1.4. Quality of Life

A Quality of Life Questionnaire (QoL) will be completed by each patient at Baseline, 4 weeks and at the end of study drug treatment (2 weeks post-RT) and reviewed and entered by the site personnel into the eCRF. The EORTC QLQ-C30 (version 3) and the EORTC QLQ-H&N43 instrument will be used for these assessments. The change from Baseline in the QoL at the end of the study will be compared between treatment groups.

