11.6. Data Monitoring Committee

An independent DMC consisting of one Biostatistician and two clinicians that includes at least one Oncologist with expertise in head and neck cancer will be formed to monitor the safety and conduct of the study on an ongoing basis. Parameters to be evaluated will include AEs (clinical and laboratory), number of dropouts overall, those withdrawals specifically due to worsening of disease, and those withdrawals due to failure to improve in a timely fashion. Data will be presented as to the DMC as treatment groups A and B to maintain the study blind. However, the DMC, as part of its charter to evaluate and ensure the safety of subjects participating in the trial, has the authority to unblind the data as appropriate.

Original: 11 January 2017 Confidential Page 55 of 67

The DMC may request any safety data including, but not limited to, SAEs, AEs, and laboratory values. The DMC may also request any efficacy data including, but not limited to the primary and secondary outcomes to evaluate benefit to risk.

The DMC will review unblinded data at the interim analyses and make recommendations to halt the trial for overwhelming efficacy, or safety concerns, or for futility; continue the trial as written; or resize the trial based on the placebo duration of SOM.

[figure not shown]

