#### 2 STUDY DESIGN

Approximately 260 patients will be enrolled into this Phase 3, placebo-controlled, double-blind, multinational study to evaluate the efficacy of SGX942 compared to placebo in treating the duration of SOM in patients receiving chemoradiation therapy (CRT) for the treatment of head and neck cancer (HNC). The study sample size takes into account the recommendation of the study Data Monitoring Committee (DMC) to increase the study sample size to 260 subjects. Up to an additional 10% may be enrolled to offset the impact of study dropouts (i.e., those subjects that do not receive 55 Gy radiation) and missing data which are each expected to potentially increase during the COVID-19 pandemic.

Patients will be randomized into one of two groups (1.5 mg/kg SGX942:Placebo) at a 1:1 ratio. They will be stratified by site, presence of gastrostomy tube, and human papilloma virus (HPV) status. Patients will receive their initial blinded intravenous (IV) study drug (1.5 mg/kg SGX942 or placebo) within 3 days following the initiation of RT.

The primary efficacy outcome for this study is the duration of SOM, defined as the number of days from the first oral examination with a WHO Grade assessment of 3 or 4 through the first day that a WHO Grade of <3 is recorded with no subsequent assessments ≥3 through the 6-week post-RT visit. Oral mucositis (OM) will be evaluated using the WHO score for OM.

[figure not shown]
Patients will be screened to assess their eligibility prior to randomization. After randomization, subjects will begin treatment with study drug within 3 days following the initiation of RT.

Patients will receive study drug while undergoing CRT and continue to receive study drug for 2 weeks after the completion of their RT. Dosing will be twice weekly. Study visit days will be every third day (+/-1 day). On study visit days, patients will receive the 4-minute infusion of study drug. Study drug will not be given on the same day as chemotherapy. Study drug can be given at any time during the visit day, but must occur on the same calendar day that is the study visit day. The twice weekly study drug treatment visit calendar extends to 2 weeks post-completion of RT.

Efficacy will be further assessed at the 3 through 6 weeks post-RT completion visits. Follow-up visits will be conducted at 6 and 12 months after the last radiation dose to continue to evaluate safety and secondary endpoints.

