#### 2.2 SECONDARY EFFICACY ENDPOINTS

## 2.2.1 Hierarchical Sequential Secondary Endpoints

Multiple endpoints in this trial are expected to be clinically important. To maintain the nominal p-value, the following five secondary endpoints will be tested in a fixed sequence, hierarchical test procedure. In this procedure, a sequential comparison of the groups for each endpoint will be calculated with unadjusted p-values. If the test is statistically significant, the null-hypothesis that the groups are the same will be rejected and testing of the next endpoint will be done. Once an analysis has a p-value above the threshold, no further endpoints will be formally tested. All 5 analyses will be conducted in the mITT population.

- 1. Comparison of the AUC for SOM (WHO Grade ≥3) by time plot (severity-weighted duration)
- 2. Comparison of the AUC for UOM (defined as WHO Grade ≥2) by time plot (severity-weighted duration)
- 3. Comparison of the incidence of SOM
- 4. Comparison of the quality of life assessment using the EORTC QLQ-C30 and QLQ-H&N43 instrument
- 5. Comparison of the total amount of opioids used

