## 3.3 METHODOLOGY AND CONVENTIONS

Safety and efficacy data will be summarized and presented by treatment group (SGX942 and placebo) in summary tables. Continuous variables will be presented by descriptive statistics including n, mean, standard deviation, median, minimum, and maximum. Categorical variables will be tabulated by frequency count and percentage.

Unless otherwise stated, all statistical tests will be two-sided hypothesis tests performed at the 5% level of significance for main effects, and all confidence intervals will be two-sided 95% confidence intervals. All analyses will be performed using SAS® Version 9.3 or higher.

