#### 9.3 ANALYSES OF SECONDARY ENDPOINTS

## 9.3.1 Hierarchical Secondary Endpoints

Multiple endpoints in this trial are expected to be clinically important. To control type 1 error, the following five secondary endpoints will be tested in a fixed sequence, hierarchical test procedure. In this procedure, a sequential comparison of the groups for each endpoint will be calculated with unadjusted p-values. If the test is statistically significant, the null-hypothesis that the groups are the same will be rejected and testing of the next endpoint will be done. Once an analysis has a p-value above the threshold, no further endpoints will be formally tested. All 5 analyses will be conducted in the mITT population. The hierarchical orders of these endpoints are:

- 1. Comparison of the AUC for SOM (WHO Grade >3) by time plot (severity-weighted duration)
- 2. Comparison of the AUC for UOM (defined as WHO Grade ≥2) by time plot (severity-weighted duration)
- 3. Comparison of the incidence of SOM
- 4. Comparison of the quality of life assessment using the EORTC QLQ-C30 and QLQ-H&N43 instrument
- 5. Comparison of the total amount of opioids used

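### Step 4 of the fixed-sequence secondary testing (quality of life) has no scale and no test, so it yields no p-value and leaves step 5 undefined; the AUC test and the link to the primary also need stating

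*SAP*

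**What the plan says.** SAP 9.3.1 gives the purpose and form of the procedure: "To control type 1 error, the following five secondary endpoints will be tested in a fixed sequence, hierarchical test procedure". SAP 2.2.1 gives the stopping rule: "Once an analysis has a p-value above the threshold, no further endpoints will be formally tested". The order is AUC for severe oral mucositis (SOM), AUC for ulcerative oral mucositis (UOM), SOM incidence, quality of life on QLQ-C30 and QLQ-H&N43, and total opioid use. The threshold comes from SAP 3.3: "Unless otherwise stated, all statistical tests will be two-sided hypothesis tests performed at the 5% level of significance for main effects".

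For step 4, SAP 9.4.5 lists 12 multi-item and 7 single-item scales, which "will be computed and summarized by visit, including change from baseline". It selects no scale and names no test. Protocol 10.2.1.4 adds: "The change from Baseline in the QoL at the end of the study will be compared between treatment groups". It too names no scale, summary score or test. Questionnaires are completed at baseline, at 4 weeks and at 2 weeks post-RT.

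For steps 1 and 2, the protocol synopsis and protocol 12.1 specify a log-rank test for AUC. Section 12.1 gives an expected non-Gaussian distribution as the reason. SAP 9.4.1 specifies a one-way ANOVA.

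On the relation to the primary, protocol 10.2.1 says: "The primary secondary endpoints are listed below in hierarchical order and will be compared in the mITT population". This orders the secondaries among themselves; it does not make a significant primary a condition for starting.

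**The concern.** A fixed sequence controls error only if every step is a single hypothesis with a single test fixed in advance. Step 4 is two whole questionnaires with descriptive output. The stopping rule needs a p-value there and none is defined, so the status of the opioid comparison depends on how someone reads the plan after the data are in.

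The AUC mismatch matters because step 1 opens everything below it: two analysts following different documents could reach different verdicts. The silence about the primary matters because a secondary claim could be made after the primary has failed, which the procedure is presumably meant to prevent.

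**Working it through.** **The plan's own threshold.** The sample size in protocol 12.4 (medians 13 v 8 days, 90% power, alpha 0.05, 1:1) confirms a two-sided level. By Freedman's formula, events = (1.960 + 1.282)² × [(13 + 8)/(13 − 8)]² = 10.51 × 17.64 ≈ 185.4, so 186, against the stated 190 evaluable. A one-sided 0.05 would give 152. Two-sided 0.05 is used below.

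**Is each step executable?**

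| Step | Endpoint | Variable fixed? | Test in SAP |
|---|---|---|---|
| 1 | AUC, SOM | yes (9.4.1) | one-way ANOVA; protocol: log-rank |
| 2 | AUC, UOM | yes (9.4.1) | one-way ANOVA; protocol: log-rank |
| 3 | SOM incidence | yes (9.4.4) | chi-square |
| 4 | Quality of life | no: 12 + 7 = 19 scales, none chosen (9.4.5) | none |
| 5 | Total opioids | yes (9.4.9) | one-way ANOVA |

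Step 4 is the only step with neither a single variable nor a test. The protocol's time point is also loose. The last questionnaire is at 2 weeks post-RT while the last study visit is at 12 months, so 2 weeks post-RT is the only workable reading.

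**What a free choice of scale would cost.** Suppose steps 1 to 3 have rejected, the drug has no effect on quality of life, and any of the 19 scales may carry step 4 at two-sided 0.05. With independent scales the false-pass rate is 1 − 0.95¹⁹ = 62.3%. With equally correlated normal test statistics (simulation, 60,000 draws):

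| Assumed correlation | Any scale significant | Any significant in the drug's favour (nominal 2.5%) |
|---|---|---|
| 0 | 62.3% | 38.2% |
| 0.5 | 40.9% | 20.4% |
| 0.7 | 28.3% | 14.0% |
| 0.9 | 15.5% | 7.8% |

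The documents give no correlation, so the range is the result.

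**AUC: log-rank or ANOVA.** Simulated null trials with 95 per arm, exponential SOM durations and SOM incidence of 60, 75 and 90% (all assumed; 4,000 trials each) gave rejection rates of 4.3-5.4% for ANOVA and 4.6-5.8% for log-rank. The verdicts differed in 1.0-1.4% of trials. A more detailed simulation used the visit schedule and the SAP 9.4.1 formula, with exponential or lognormal durations and effects at or near 13 v 8 days (complete data, 3,000 trials per scenario). There the two tests disagreed at step 1 in 1.5-2.4% of trials if every patient has SOM, 4.7-4.8% at 85% incidence and 7-9% at 70%.

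**If the chain is not gated on the primary.** Under no drug effect, any false secondary claim must pass step 1. The family error is therefore P(|Z1| > 1.96 or |Z2| > 1.96) = 0.10 − P(both), where Z1 is the primary and Z2 is step 1. Both derive from the same WHO scores, so the correlation is high; the values are assumed:

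| Correlation | At least one false claim | In the drug's favour (nominal 2.5%) |
|---|---|---|
| 0.86 | 7.4% | 3.7% |
| 0.90 | 7.0% | 3.5% |
| 0.95 | 6.5% | 3.2% |
| 0.98 | 5.9% | 3.0% |

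**The case against.** Several things can fairly be said for the plan.

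- **Step 5 need not be blocked.** The chain stops on a p-value above the threshold. If quality of life is only descriptive, one may skip it and run steps 1, 2, 3 and 5, which is still a valid fixed sequence. That stands, and it is why this point does not call step 5 unreachable. But the SAP does not say so, and it lists quality of life among the five formally tested endpoints.
- **The SAP may govern the AUC test.** Protocol 12.1 defers full detail to the SAP. That is a reasonable claim, but the same section itself states log-rank and gives a distributional reason, so the change should be acknowledged.
- **The missing gate is an argument from silence.** Protocol numbering runs from 12.1 to 12.3, and section 12.2 is not in the available text; it may contain the condition. This stands. The point is only that the SAP, to which protocol 12.1 refers for the order of importance, should state it.

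A reader might also infer stronger things that the documents do not support.

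- **That the AUC mismatch inflates type I error.** It does not: each test holds about 5%.
- **That AUC after withdrawal is subject to three conflicting rules.** Protocol 10.2.1.1 and 10.2.1.2 and SAP 9.4.1 all sum to the last recorded score. That can be read as consistent with the censoring in protocol 7.3. The last-value-forward remark in SAP Appendix 1, item 5 is background in a COVID-19 section. Appendix 1, item 4 is headed for SOM duration and already gives sensitivity analyses for that. What remains is a clarification for patients who withdraw while in SOM or UOM.
- **That 62% is the trial's false-positive rate.** It applies to step 4 alone, once steps 1 to 3 have rejected and if the scale is chosen freely.

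**Conclusion.** The point holds in this form: the sequence cannot be carried out as written at step 4, and the status of step 5 is left to interpretation. That is a gap in the text and needs no assumption. The 15-62% false-pass range is conditional on free choice among 19 scales, on steps 1 to 3 rejecting, and on assumed correlations.

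The AUC mismatch is a reconciliation item. It adds no error, but in the assumed scenarios it could change the step 1 verdict in roughly 1-3% of null trials and 1.5-9% of trials near the design effect.

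The absent gate is modest: about 6-7% instead of 5%, or 3.0-3.7% instead of 2.5% in the drug's favour. It applies only if protocol 12.2 does not already supply the condition.

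The primary analysis and its sample size are unaffected. This should be corrected, chiefly to protect the secondary claims and the opioid claim in particular.

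**What to change.** Before unblinding:

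1. **SAP 9.4.5.** Name one quality-of-life scale (the sponsor's choice), change from baseline to 2 weeks post-RT, and one between-group test; make all other scales descriptive. Alternatively, remove quality of life from the chain so that opioid use becomes step 4.
2. **SAP 2.2.1 and 9.3.1.** State that step 1 is tested only if the primary is significant at its final two-sided level. That level is 0.05, or what remains after any interim alpha spending, since protocol 11.6 says: "The DMC will review unblinded data at the interim analyses and make recommendations to halt the trial for overwhelming efficacy".
3. **Protocol synopsis and 12.1, SAP 9.4.1.** Reconcile to one AUC test and keep the other as a sensitivity analysis.
4. **SAP 9.4.1, optional.** Say whether summing to the last recorded score applies to patients who withdraw while in SOM or UOM, and extend the sensitivity analyses of Appendix 1, item 4 to AUC.

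With items 1 to 3 in place, each hypothesis is tested once at the final level in a fixed order after the primary, so the error over the primary and the secondaries in the chain is at most 5%.

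The cost is wording only, with no new data or patients. The sponsor must commit to one scale in advance or give up quality of life's place in the chain, and formal secondary claims are lost if the primary fails.

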#### 9.4.6 Cumulative Treatment Break Duration

The cumulative duration of treatment breaks for each patient will be calculated by summing the actual number of treatment break days (≥3 days break) through the final RT treatment and will be compared between treatment groups using a one-way ANOVA test.

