- Tumors of the lips, sinuses, salivary glands, nasopharynx, hypopharynx, or larynx
- Evidence of significant renal, hepatic, hematologic, or immunologic disease determined by any
 one of the following: (the below are examples of evidence of significant disease, not required
 tests)
 - A. Estimated creatinine clearance <30 mL/min

 - B. ALT or AST level greater than 10-fold the upper limit of normal or total bilirubin greater than 3-fold the upper limit of normal
 - C. Manifestations of end-stage liver disease, such as ascites or hepatic encephalopathy
 - D. Thrombocytopenia (less than 60,000 cells/mm³)
 - E. CD4+ T cell count below 200 cells per μL (verification only required if there is a clinical diagnosis of HIV infection)
- 9. Evidence of immediate life-threatening disease or a life expectancy of less than 3 months
- 10. Women who are pregnant or breast-feeding
- 11. Participation in any study involving administration of an investigational agent within 30 days of randomization into this study
- 12. Any condition that, in the opinion of the Investigator, would compromise the safety of the subject or quality of the data

Investigational Product, Dosage, and Mode of Administration:

Dusquetide is a pentapeptide that is a first in class Innate Defense Regulator (IDR). SGX942 is dusquetide formulated for IV infusion.

The diluted solution will be administered as a 4-minute IV infusion using an infusion or syringe pump. Patients will be treated twice a week (2-4 calendar days apart) starting within 3 days after initiating RT and continuing through 2 weeks after completion of the RT. Patients missing more than 5 sequential scheduled RT sessions will be withdrawn from the trial.

Duration of Treatment:

Patients will start study drug infusions within 3 days after starting RT and continue through 2 weeks after completion of RT. RT is typically scheduled to continue for 5 to 7 weeks, if there are no breaks in treatment. Since distinct treatment breaks of up to 1 week may be encountered, the expected study drug treatment duration will be from 6 to 11 weeks.

Reference Therapy, Dosage, and Mode of Administration:

Placebo will consist of 0.9% sodium chloride (normal saline) that is identical in appearance to active drug. Blinded vials of placebo will be diluted identically to that of active drug to a final volume of 25 mL and infused using an infusion or syringe pump over 4 minutes. The frequency and duration of therapy will be identical to the active drug.

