7.3. Patient Withdrawal Criteria

Patients have the right to withdraw from this trial at any time (as described in the informed consent document) without prejudice to further care. An investigator may withdraw a patient from the study at any time for any of the following reasons:

- The patient withdraws his/her consent or refuses follow-up evaluations.
- The patient is lost to follow-up and will not attend further study visits.
- The investigator determines that further participation would be detrimental to the patient's health or well-being.
- The patient fails to comply with the study requirements to cause harm to self or seriously interfere with the validity of the study results.
- The female patient becomes pregnant during the treatment period. In this case, treatment should be halted and the patient followed until the end of the pregnancy. If a child is born, the infant should be followed through at least 6 months of age.
- At the discretion of the site investigator if he/she feels that it is in the best medical interest of the patient.
- The patient misses more than 5 consecutive scheduled RT sessions.
- Patients withdrawn from the study will have as many of the trial assessments completed
 as the patient permits including blood tests and scans but not including OM scoring. All
 other therapies including radiation therapy, the type and frequency of chemotherapy, and
 oral treatments will remain at the discretion of the clinical team. Patients will be censored
 in the efficacy analyses at the time of withdrawal.
- Patients withdrawn from the trial will not be replaced but enrollment will continue until a minimum of 260 patients have been enrolled.

7.4. **Termination of the Study**

The study may be terminated early for any of the following reasons:

- A health authority or DMC requests termination of the study.
- It has been determined that the risk level associated with the experimental drug is significant and warrants termination of the study.
- Soligenix, for reasons other than safety, may terminate the study at any time by written notice of intended termination provided at least thirty (30) days prior to termination.
- The investigator or IRB/EC, for reasons other than safety, may terminate participation of this site in the study by written notice of intended termination provided at least thirty (30) days prior to termination.

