10.2.2.1. Cumulative Number of Treatment Breaks

For the analysis purposes for this study, treatment breaks will be defined as missing 3 or more scheduled consecutive RT treatment sessions. The cumulative duration of treatment breaks for each patient will be calculated by summing the actual number of treatment break days (≥3 days per break) through the final RT treatment and comparing these between treatment groups.

10.2.2.2. **Duration of SOM in the ITT Population**

Using the above definitions, the duration of SOM will be compared between treatment groups in all patients randomized (ITT population).

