## 1.2.2 Additional Secondary Objectives

- To assess the impact that SGX942 has on the cumulative number of days of RT breaks
- To assess the impact that SGX942 has on the duration of SOM; in all randomized patients receiving fractionated RT and concomitant cisplatin chemotherapy, given as 80-100 mg/m^2
- To assess the impact that SGX942 has on the duration of UOM
- To assess the impact that SGX942 has on the cumulative amount of pain reported by patients

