#### 9.3.2 Other Secondary Endpoints

- Comparison of the cumulative number of days of RT breaks (mITT population)
- Comparison of the duration of SOM; in all randomized patients receiving fractionated RT and concomitant cisplatin chemotherapy, given as 80-100 mg/m² (ITT population)
- Comparison of the duration of UOM (mITT population)
- Comparison of the cumulative amount of pain reported by patients (mITT population)

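### The RT-break endpoint scores a permanent stop of radiotherapy as 0, better than a 3-session pause, and gives breaks of more than 5 sessions no single score

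*SAP*

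**What the plan says.** The objective in SAP 1.2.2 reads: "To assess the impact that SGX942 has on the cumulative number of days of RT breaks". Protocol 10.2.2.1 sets the counting threshold: "treatment breaks will be defined as missing 3 or more scheduled consecutive RT treatment sessions". SAP 9.4.6 derives each patient's total by "summing the actual number of treatment break days (≥3 days break) through the final RT treatment" and says that the totals "will be compared between treatment groups using a one-way ANOVA test". Neither section caps the total.

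SAP 9.3.2 assigns this comparison to the mITT population, which SAP 3.2.3 limits to randomised patients with at least one dose of study drug and at least 55 Gy. SAP section 9 adds sensitivity analyses in the ITT and PP populations. The ITT population (SAP 3.2.2) has no radiation minimum.

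Three statements on withdrawal also bear on the endpoint:

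- The protocol synopsis is mandatory: "Patients missing more than 5 sequential scheduled RT sessions will be withdrawn from the trial".
- Protocol 7.3 lists the same trigger, "The patient misses more than 5 consecutive scheduled RT sessions", but under a lead-in that leaves withdrawal to the investigator.
- Protocol 7.3 also censors withdrawn patients "in the efficacy analyses at the time of withdrawal", while allowing RT to continue and asking for trial assessments other than mucositis scoring as far as the patient permits.

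**The concern.** The objective is about disruption of RT, and the severest form of disruption is giving RT up. A sum that ends at the last treatment cannot register that, because the untaken fractions all fall after the end of the window. The patient gets the best possible score, tied with a patient who never missed a session.

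The mITT restriction adds a second difficulty. Whether a patient reaches 55 Gy is decided after randomisation and can itself result from RT disruption, so the main analysis selects patients partly on the outcome that it measures. Protocol 12.5 recognises this route for the primary endpoint. Early stops are also expected: protocol 6.1 says that some patients will stop early, and SAP section 2 treats failure to reach 55 Gy as dropout that may rise during the pandemic.

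Third, the plan does not say what total a patient has after a break long enough to trigger withdrawal. An ANOVA needs one complete number per patient and cannot use a censored one.

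At stake is whether a difference between arms, or the lack of one, can be read as an effect on disruption. It could instead reflect patients moving between stopping (scored 0) and pausing then finishing (scored 3 or more).

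**Working it through.** The documents give no standard deviation, effect size, event rate or power for this endpoint, so there is no plan figure to reproduce. The check is to apply the stated rules to constructed patterns.

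**Inputs**

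- Fraction size 2.0 to 2.2 Gy, total 55 to 72 Gy (protocol 7.1).
- Five sessions a week for 7 weeks (Schedule of Events), so 7 × 5 = 35 fractions. At 2.0 Gy this is 35 × 2.0 = 70 Gy, inside the permitted range. The 35-fraction, 2.0 Gy plan is an assumption for illustration.
- Threshold: runs of 3 or more consecutive scheduled sessions missed.
- Window: to the final RT treatment, read as the last one delivered. The Schedule of Events likewise times post-RT visits from the last RT.
- Break days counted as missed sessions (assumption; see the end of this section).
- mITT: at least 55 Gy. At 2.0 Gy, 27 × 2.0 = 54 Gy falls short and 28 × 2.0 = 56 Gy qualifies. At 2.2 Gy, 25 × 2.2 = 55 Gy qualifies.

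**Formula.** Score = sum of the lengths of all runs of at least 3 missed sessions that begin before the last delivered fraction. Under the censoring reading, counting stops at the 6th session of the first run longer than 5.

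| Pattern | Missed or undelivered | Score, summed to final RT | Score, censored at withdrawal | Dose (Gy) | In mITT |
|---|---|---|---|---|---|
| Stops for good after fraction 28 | 35 − 28 = 7 | 0 | 0 | 56 | yes |
| Stops for good after fraction 27 | 35 − 27 = 8 | 0 | 0 | 54 | no |
| One 3-session break, completes | 3 | 3 | 3 | 70 | yes |
| Three 5-session breaks, completes | 15 | 15 | 15 | 70 | yes |
| One 10-session break, completes | 10 | 10 | 6 | 70 | yes |
| 5-session then 10-session break, completes | 15 | 15 | 5 + 6 = 11 | 70 | yes |
| Two missed a week for 6 weeks, completes | 2 × 6 = 12 | 0 | 0 | 70 | yes |

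**Results**

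1. *Permanent stops.* The first and third rows are ranked in the wrong order: 7 fractions never given score 0, and a 3-session pause with full delivery scores 3. This does not depend on how the withdrawal rule is read.
2. *The 55 Gy condition.* The second patient is outside the main analysis. The ITT sensitivity analysis readmits the patient, still with a score of 0 for 8 undelivered fractions.
3. *Long breaks.* A 10-session break scores 10 if SAP 9.4.6 governs, and 6 if the patient is withdrawn and the censoring in protocol 7.3 governs. The synopsis and protocol 7.3 differ on whether withdrawal must follow, so the text does not settle the score.
4. *Repeated breaks.* Breaks of 3 to 5 sessions trigger no withdrawal and add in full: 5 + 5 + 5 = 15.
5. *Unit.* Protocol 10.2.2.1 defines a break in sessions and then sums days. SAP 9.4.6 speaks only of days. The two differ: 6 consecutive missed sessions at 5 a week include at least one weekend, so they span at least 6 + 2 = 8 calendar days.

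**The case against.** The strongest reply is that the objective concerns days of RT breaks, and a permanent stop is a different construct. The 3-session threshold is explicit and prespecified, and the defined comparison can be computed. The endpoint lies outside the five-step hierarchy, so no error-controlled claim rests on it. Patients below 55 Gy do appear in the ITT sensitivity analysis, and SAP section 4 reports premature discontinuations by reason. Protocol 12.5 argues that any bias from the 55 Gy restriction works against SGX942.

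Much of this stands. The threshold is a legitimate choice: scattered misses scoring 0 is a consequence of it, and preferring another threshold is not a correction. Three stronger readings that a reader might draw also fail:

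- *That about 6 days is a ceiling on the score.* The withdrawal trigger applies to one run, not to the total. Repeated shorter breaks reach 15 in the table, and even the censored reading gives 11 for a 5-session break followed by a 10-session one. The synopsis itself anticipates separate breaks of up to a week.
- *That patients under 55 Gy are never analysed.* They are missing from the main analysis only.
- *That the objective cannot be answered, or that the treated arm would look worse.* The documents give no frequency for any pattern, so neither the size nor the direction of bias follows.

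The reply does not remove the reversed ranking. Treating stops as a separate construct would justify reporting them separately; it does not justify entering them as 0 in a comparison of disruption. The ITT sensitivity analysis keeps the same 0. The argument in protocol 12.5 concerns the duration of severe mucositis and supposes that the drug reduces dropout, so it does not fix the direction here.

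**Conclusion.** The concern holds in a limited form. By the stated rules, an unplanned permanent stop adds 0 however many fractions are left, and so ranks better than a completed course with one qualifying break. The main analysis also conditions on a post-randomisation dose that disruption can determine. Breaks of more than 5 consecutive sessions have no single score, and the planned ANOVA cannot take a censored one.

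In the worked cases the gap is 7 undelivered fractions scored 0 against a 3-session pause scored 3, and 6 against 10 for the same 10-session break. These figures assume 35 fractions of 2.0 Gy and days counted as sessions. The ranking of stops below pauses needs only the stated window and threshold. The effect on the between-arm difference cannot be calculated from the documents. As this is a stated objective but not part of the formal testing sequence, the point should be corrected but does not threaten the trial's main conclusion.

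**What to change.** In SAP 9.4.6, with matching wording in protocol 10.2.2.1:

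- Count planned fractions left undelivered after an unplanned permanent stop as missed sessions.
- Make the ITT population with a Wilcoxon rank-sum test the main analysis, and keep the current definition in mITT as supportive.
- State that RT delivery data are used after withdrawal from the trial where the patient permits, so that the censoring in protocol 7.3 does not apply to this endpoint.
- State whether break days are sessions or calendar days.
- Keep the 3-session threshold, and add a count of all missed sessions as a supportive summary.

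Reconcile the synopsis with protocol 7.3 on withdrawal, and protocol 7.3 with SAP 9.4.6 on censoring. No clinical rule needs to change for this.

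The cost is a small wording change in both documents. Delivered dose is already needed to establish 55 Gy, but the planned number of fractions must also be available from the RT record, and neither document says that it is captured. Data after withdrawal may be incomplete. Reported disruption will be higher in both arms.
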